3.1. Confidence Intervals and p-values

All calculated p-values will be two-sided and compared to a 5% significance level. If a p-value is less than 0.05, the corresponding treatment group difference will be denoted as statistically significant. All estimates will be presented with two-sided 95% confidence intervals. No

adjustments of type one error for multiplicity testing are planned because the goal of the trial is to detect any potential safety issues instead of confirming and investigating a safety concern.

3.2. Treatment Emergent AE definition

The information on adverse events will be collected from the time of signing ICF. The treatmentemergent adverse events (TEAEs) will be defined as events occurring from administration of study drug or events starting before study drug administration but worsening after study drug administration to 4 months post-treatment.

3.3. Handling of AE missing dates or severity

Partial adverse event dates will be imputed with reference to dose intake date and follow up end date. If complete (imputed) AE end date is available and the imputed AE start date is later than the (imputed) AE end date, then imputed AE start date should be set to the (imputed) AE end date. *TEAEs are from administration of study drug to 4 months post-treatment*. Missing AE start dates will be imputed with the dose intake date unless the end date suggests it could have started prior to the dose intake. For the end date that is completely missing, if the AE has stopped and start date is prior to the dose intake then impute with the date of dose intake, if AE started on or after the dose intake then impute with the last follow up date. A conservative approach will be used in the missing date imputation for such AEs to be defined as treatment emergent. More details on the imputation procedure will be provided in the programming specification.

For the missing severity grade, severe or grade 3 will be used though it is not expected to have AE severity missing.

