## 8.1.2. Assessments post study drug administration

## 8.1.2.1. Assessments during observation period at the hospital

The following procedures will be performed every day throughout the hospitalisation period:

- Collection of concomitant medications
- Collection of AEs

## Assessment at Day 1

• Blood pressure will be taken 4 hours (± 1 hour) and 9 hours (± 1 hour) after the study drug administration.

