The AE can occur in both periods for the same subject (i.e. the event is still present at the second time period). However, for the period analysis the AE start date will be used to identify AEs in each period. The denominator of occurrence rate in each period will respectively be the number of subjects who receive at least one tablet of study treatment during the first time period and the number of subjects attending the 4-month visit or have reported a TEAE during the second time period. All statistics will be provided per time period to separately assess and interpret early events probably attributed to study treatment and late events that could be attributed to the disease or are persistent.

The time course of treatment effect will be analysed using the log rank test stratified by study centre and will be performed on the time to occurrence of TEAEs, taking into account the attrition rate of subjects who are being followed up. A loss to follow-up or a withdrawal will be censored at the time of the last attended visit. The Kaplan-Meier estimates of the proportion of subjects without any TEAE in each treatment group will be presented graphically to assess the time course of the response.

The hierarchy of testing reflects the sequence of testing from the more general effect to the most specific effect. There is a multiplicity of testing issue and an inflation of type I error that cannot be discarded. However, no adjustments of type I error are planned for this study as this study has been designed to detect any potential safety issues rather than confirming and investigating a safety concern.

The rate of occurrence of AEs will be analysed by the true positive status (subjects with parasites detected during the follow up period) in either treatment or placebo groups.

The rate of conversion to parasite positive and the rate of return to seronegative over 4 months will be analysed descriptively using frequency and proportion by treatment group.

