5.1. Primary Objective Analysis

The assessment of the safety of a single dose of acoziborole compared to placebo during a follow up period of 4 months will be conducted using excess rate (ER) of occurrence of any TEAE over the first 4 months in the acoziborole group compared to placebo. The numerator of the occurrence rate will be the number of subjects with at least one TEAE and the denominator will be the number of subjects in the Safety Set. In addition, a sensitivity analysis will be performed on safety set population excluding subjects with treatment misallocation. The ER is the occurrence rate of any TEAE in the acoziborole group minus the occurrence rate in the placebo group. The 95% confidence interval (CI) of the excess rate will be calculated using Wilson score interval (which provides average coverage very close to 95% in all cases⁹). The excess rate (ER) of occurrence of any TEAE will be transformed to the number of subjects needed to treat (NNT) to observe one more subject with a TEAE in the acoziborole group compared to placebo (NNT = 1 / ER).

The analysis will be performed on the total SS population and by age groups (defined as adolescents aged 15-17 years and adults aged \geq 18 years), gender, TEAE severity category and period of occurrence. Four categorizations of TEAEs per severity will be derived as 1) Serious AEs regardless of the relationship to drug, 2) severe and related to drug TEAEs and 3) mild and/or moderate regardless of relationship to drug, and 4) severe but not related to drug. TEAEs period of occurrence will be categorized as: 1) Occurrence during the hospitalization period and 2) Occurrence after the hospitalization period (from EoH to month 4). The same event for the same subject can occur at both periods (i.e., the event is still present at the second period). However, for the analysis the AE start date will be used to identify AEs in each period. The denominator of occurrence rates will be the number of subjects receiving at least one tablet of IP for the first period and the number of subjects attending the 4-month visit or having reported a TEAE during the second period.

The occurrence rate analysis will be performed on a safety set. MedDRA preferred terms of TEAE with occurrence rates ≥1% in one treatment group will be compared between treatment groups on the excess rates and NNT for any TEAE, by TEAE severity to assess whether the more severe

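### Dating an AE with a completely missing start date to the day of dosing suits the treatment-emergent flag, but tends to move late events into the hospital period and to Day 1 of the time-to-event curve

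*SAP*

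**What the plan says.** - **Missing start dates.** SAP 3.3: "Missing AE start dates will be imputed with the dose intake date unless the end date suggests it could have started prior" to dosing. The exception looks only backwards. Neither a late end date nor the visit at which the event was first reported changes the result.
- **Purpose.** SAP 3.3: "A conservative approach will be used in the missing date imputation for such AEs to be defined as treatment emergent".
- **Partial dates.** These have a separate rule, "Partial adverse event dates will be imputed with reference to dose intake date and follow up end date", with no algorithm given. SAP 3.3 adds: "More details on the imputation procedure will be provided in the programming specification".
- **Period split.** SAP 5.1: "for the analysis the AE start date will be used to identify AEs in each period". The periods are hospitalisation, and discharge to Month 4. Protocol 10.7.1 also uses the start date.
- **Reason for the split.** Protocol 10.7.1 wants to separate "early events probably attributed to study treatment and late events that could be attributed to the disease or are persistent".
- **Time course.** SAP 5.1 and Protocol 10.7.1 plan a stratified log-rank test and Kaplan-Meier curves on time to TEAE.
- **AE collection.** Protocol 8.1.2.1 lists AE collection under "The following procedures will be performed every day throughout the hospitalisation period". After discharge, Protocol 8.5.4 relies on questioning at follow-up visits. Table 1 shows these at Months 1 and 4.

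**The concern.** One imputed date serves three purposes: the treatment-emergent flag, the period label and the event time. Day 1 is a cautious choice for the first. It is not cautious for the other two, because it takes the event out of the late period.

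In hospital, staff ask about AEs every day, so an unknown onset should be uncommon. After discharge, onset is recalled weeks later. A completely missing start date is therefore more likely to belong to a late event. No document reports this; it is an inference from the collection schedule.

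At stake is the reading of the period table. Late events would be counted among those that the protocol describes as "early events probably attributed to study treatment". Late effects cannot be ruled out in advance: SAP 1.1 gives a half-life of about 400 hours, and Protocol 3.3 ties the Month 4 visit to clearance of the drug.

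**Working it through.** The plan gives no figure for missing AE dates, so there is nothing of its own to reproduce.

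**1. Following the rules.** Take an event first reported at Month 4, with no start date and no end date pointing to a pre-dose start. SAP 3.3 dates it Day 1. SAP 5.1 then places it in the hospital period, and the log-rank and Kaplan-Meier analyses take it as an event on the day of dosing. This happens even if every daily hospital review found nothing. Treatment-emergent status needs only a date on or after dosing, so Day 1 is not required for the flag.

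**2. Inputs.** From the documents: 900 acoziborole and 300 placebo subjects. Assumed: e, the true hospital-period rate; L, the share of subjects with a late TEAE, independent of e; m, the chance that the late event has no start date.

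Subjects with a true hospital TEAE are already counted there, so:

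- observed hospital rate = e + (1 − e) × L × m
- added share = (1 − e) × L × m

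**3. Number moved, with e = 10% and L = 40%.**

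| m | Added share | Of 900 | Of 300 | Relative to e |
|---|---|---|---|---|
| 2% | 0.9 × 0.40 × 0.02 = 0.72% | 6.5 | 2.2 | 7.2% |
| 10% | 0.9 × 0.40 × 0.10 = 3.6% | 32.4 | 10.8 | 36% |

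**4. Sensitivity to e and L.** With e = 5% and m = 10%, the added share is 0.95 × L × 0.10. That is 0.95%, 2.85% and 4.75% for L = 10%, 30% and 50%. Misdated subjects would then be 16%, 36% and 49% of those counted in the hospital period. With m = 1%, the same shares are 2%, 5% and 9%.

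**5. Effect on the planned contrast (excess rate, ER).**

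- *True early effect, equal missingness.* Early rates of 10% and 5%, L = 30% in both arms, m = 10%. Acoziborole: 0.10 + 0.90 × 0.30 × 0.10 = 12.7%. Placebo: 0.05 + 0.95 × 0.30 × 0.10 = 7.85%. The ER goes from 5.0% (Wilson-based 95% CI 1.4 to 7.9) to 4.85% (0.7 to 8.3). The risk ratio falls from 2.00 to 1.62, but it is not a planned measure for the period table.
- *Late effect only.* Early rate 5% in both arms, L = 35% and 25%, m = 10%. The early ER is 0.95 × (0.35 − 0.25) × 0.10 = 0.95 points (CI −2.9 to 4.1) where the truth is zero. At m = 20% it is 1.9 points.
- *Unequal missingness, no true effect.* L = 30%, m = 10% and 5%. The early ER is 0.95 × 0.30 × (0.10 − 0.05) = 1.4 points.

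**6. Effect on the log-rank test.** An unstratified simulation used 300 runs per setting, e = 5% and L = 30% in both arms. Rejection was 5.3%, 6.7% and 4.3% at m = 0, 10% and 20%. The Monte Carlo standard error is √(0.05 × 0.95 / 300) = 1.3 points, so type I error stays near 5%. The share of the acoziborole arm with an event by Day 5 rose from 5.0% to 7.8% and 10.8%.

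**The case against.** The case against has real force.

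- **The main result is safe.** A reader might infer that the rule biases the primary comparison. It does not: an event moved to Day 1 is still a TEAE, so the 4-month any-TEAE excess rate, its NNT and the CMH test are unchanged.
- **The protocol's attribution wording is limited.** A reader might infer that the protocol ascribes an early drop in the Kaplan-Meier curve to treatment. Protocol 10.7.1 makes that remark about the per-period statistics only. The curve is there to show the time course.
- **Few events may be affected.** Partial dates have their own rule, and a recalled event may well yield a month. Protocol 8.5.4 requires an onset date in the CRF, and Protocol 12.5 has monitors check completeness.
- **The contrast is robust under blinding.** With equal missingness and no late effect, the early excess rate hardly moves.
- **The specification may narrow the rule.** It is not among the documents.

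All of this limits the size and reach of the point; none of it removes the point. As the SAP stands, the default is Day 1, it feeds the period and time-to-event analyses, and no sensitivity analysis for imputed dates is planned.

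**Conclusion.** The point holds for the period table and the time-to-event analysis. The rule goes further than its stated purpose and tends to place undated late events where they are less likely to have begun.

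Under the assumed 10% hospital rate, independent 40% late rate and 2-10% of late events undated, 0.7-3.6% of subjects would be added to the hospital period: about 6-32 of 900 and 2-11 of 300, or up to 36% relative inflation. None of these three inputs comes from the documents, and the true missing-date rate may be small. The late-period rate need not fall by the same amount, because a subject with another, dated late TEAE still counts there.

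A reader might go on to infer that the rule manufactures an early drug effect. The documents do not support that. A material between-arm distortion needs a true late effect or unequal missingness in a double-blind trial, and neither is shown. What is established is inflation of the early rate within each arm, and partial leakage of a late effect if one exists.

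**What to change.** In SAP 3.3, separate the uses of the imputed date:

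1. Keep the present conservative rule for the treatment-emergent flag.
2. For the period and time-to-event analyses, date an event with a completely missing start no earlier than the day after the last AE assessment before it was first recorded, and not after its end date. This applies only if the eCRF holds the first-recording visit, which the documents do not confirm.
3. In any case, report the number of imputed start dates by arm, and repeat the period table and the time-to-event analysis without those events.

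The cost is SAP and programming-specification wording and a little more programming. No new data are needed if the visit field exists; if it does not, step 3 alone shows whether the issue matters. The drawback is a less conservative early attribution in the main period table. The gain for the curve is also limited for events first recorded at Month 1: if the last hospital assessment was on Day 5, they move only from Day 1 to about Day 6.

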3.4. Analysis Populations

The analysis populations are described separately for subject disposition, main study analysis population for the primary objective and sub-study for exploratory objective analysis population.

3.4.1. Subject Disposition populations

The Screened set includes all subjects who were screened and provided informed consent by signing the ICF.

Intent-to-Treat set (ITT) includes subjects who signed the informed consent and were considered eligible by the investigator and randomized into the study, i.e., randomized to receive acoziborole or placebo. Data should be reported based on the treatment to which subjects were randomly assigned (i.e., regardless of the actual treatment received).

The Treated set includes all randomized subjects who received three tablets of IP (placebo or acoziborole).

PK analysis set includes all randomized subjects who received at least one tablet of IP (placebo or acoziborole) and for whom at least one blood sample for pharmacokinetics is available.

Modified ITT (mITT) is composed of all ITT subjects who received at least one tablet of IP (placebo or acoziborole). Data should be reported based on the treatment to which subjects were randomly assigned (i.e., regardless of the actual treatment received).

3.4.2. Main study analysis populations

Safety set of subjects (SS) is composed of all subjects in the PK analysis set. This analysis population will be the primary set of subjects for the main study analyzed per the actual treatment received. Actual treatment received will be determined by detection/non-detection of acoziborole in blood through PK analysis. Additional primary analysis will be performed using the safety set of subjects excluding subjects with treatment misallocation.

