## 9. Withdrawal criteria

## 9.1. Subject withdrawal from the study

A subject may withdraw from the trial at any time at their own request or may be withdrawn at any time at the discretion of the Investigator or Sponsor for safety, behavioural, or administrative reasons.

If a subject does not return for a scheduled visit, every effort should be made to contact the subject.

In any circumstance, every effort should be made to document subject outcome, if possible.

If the subject withdraws consent, no further evaluations should be performed and no attempts should be made to collect additional data, with the exception of safety data, which should be collected if possible and in accordance with subject consent.

If a subject withdraws from the study, and the reason is provided, this should be documented in the source note.

If a subject is withdrawn from the study because of a treatment limiting AE, thorough efforts should be made to clearly document the outcome of AE.

If a subject is withdrawn from the trial, the Investigator will make all necessary arrangements

to ensure that the subject receives the appropriate treatment for any relevant medical condition that may have caused the withdrawal.

Subjects withdrawn from the study will not be replaced.

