# 9.2. Subjects lost to follow-up

If a subject misses the 4-month visit (-10 days to +1-month window) and can no longer be contacted by the study personnel, she/he will be considered as lost to follow-up. Before the subject can be considered as lost to follow-up, the study personnel must make every effort to re-establish contact with the subject or relatives as soon as possible to advise him/her of the importance of continuing in the study and to ascertain whether or not s/he wishes to and/or should continue in the study. These contact attempts should be documented in the participant's medical record.

A subject declared as lost to follow-up was replaced in order to maintain the planned sample size. From 5 months after the start of the study, the rate of subjects lost to follow-up was regularly assessed to ensure 1200 subjects will complete the 4 months of follow-up. However, given the low rate of lost to follow-up subjects after 1.5 year of study conduct, it was agreed that not replacing the subjects lost to follow-up will not impact the statistical power of analysing the primary objective since the subjects will be included in the safety analysis set.

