## 10.2. Definition of study populations included in the analysis

For the main safety study, the study population that will be used for the analyses is defined as below:

• **Safety set of subjects** (SS) is a modified intent to treat (mITT) set of subjects composed of all randomised subjects who received at least one tablet of IP (placebo or acoziborole).

For the TrypSkin sub-study, the study populations that will be used for the analyses are:

- **Primary set of subjects** for exploratory efficacy analyses is the mITT set composed of subjects, who participate in the TrypSkin sub-study and who receive at least one tablet of IP (placebo or acoziborole).
- Secondary set of subjects for exploratory efficacy analyses is the set of all seropositive subjects who are positive for the presence of trypanosomes by at least one molecular diagnostic test in the skin, blood and/or DBS at baseline.

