#### 10.7. Safety analysis

#### **10.7.1.** Primary endpoint analysis

Adverse events will be coded using the Medical Dictionary for Regulatory Activities (MedDRA) SOC and PT. Occurrence rates of each TEAE (≥1%), by MedDRA PT, will be compared.

The primary endpoint for this study is the occurrence of TEAEs from administration of study drug to 4 months post-treatment. It is a binary endpoint (presence or absence of any TEAE).

The primary outcome measure is the ER of TEAEs over the first 4 months post-treatment in the acoziborole group compared with placebo. The occurrence rate will be the number of subjects with at least one TEAE as the numerator and the number of subjects who receive at

least one tablet of study medication (the SS) as the denominator. Loss of subjects to follow-up and withdrawal for a reason unrelated to safety or tolerance will not be considered as AEs.

The ER of occurrence of any TEAE will be transformed to the number of subjects needed to treat (NNT) to observe one more subject with a TEAE in the acoziborole group compared with placebo (NNT=1/ER).

The Cochran-Mantel-Haenszel test, stratified by study centre, will be used to compare the occurrence rate of TEAEs between treatment groups. The same test will be applied to the primary endpoint and each component of the composite endpoint (common TEAEs based on PTs).

Generalisability of the treatment effect will be assessed using a test of homogeneity of the odds ratio (OR) across study centres. If the number of randomised subjects in each study centre reaches 100, each study centre will be considered as a stratum. If one or several study centres has fewer than 100 subjects, the smallest study centres will be pooled together to obtain strata of at least 100 subjects. If the test of homogeneity is not significant, the common OR and the 95% CI will be estimated. If the hypothesis of homogeneity is rejected, the OR per study centre will be provided.

Treatment-emergent AEs will be categorised by severity.

All statistics will be provided to ensure that the most pertinent events (serious and severe) are not "lost" amongst non-serious and non-severe events.

Treatment-emergent AEs will also be categorised by period of occurrence during the study. Two successive periods of time will be considered:

- Occurrence during the hospitalisation period
- Occurrence or prevalence after the hospitalisation period (from discharge to Month 4).

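### The SAP's Safety Set requires an available PK sample, so a dosed subject with neither a Day 5 nor a Month 1 sample drops out of the primary safety comparison that the protocol bases on all dosed subjects

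*SAP*

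**What the plan says.** **Protocol.** Section 10.2 defines the Safety Set as "all randomised subjects who received at least one tablet of IP (placebo or acoziborole"). Section 10.7.1 takes as the primary denominator the subjects who receive at "least one tablet of study medication (the SS) as the denominator". Neither sets a PK condition. Section 9.2 explains why subjects lost to follow-up are no longer replaced: stopping replacement "will not impact the statistical power of analysing the primary objective since the subjects will be included in the safety analysis set".

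**SAP.** Section 3.4.2 states: "Safety set of subjects (SS) is composed of all subjects in the PK analysis set". Section 3.4.1 limits the PK analysis set to randomised subjects who took at least one tablet and "for whom at least one blood sample for pharmacokinetics is available". Section 5.1 uses this Safety Set as the primary denominator, and section 5.2.1 uses it for the all-AE comparison.

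Section 3.4.4 gives the background. Treatment misallocation was found during the study, so actual treatment is read from PK: the Day 5 sample or, failing that, Month 1. It gives no rule for a subject with neither.

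One further run is planned: "Additional primary analysis will be performed using the safety set of subjects excluding subjects with treatment misallocation". The SAP also defines an all-dosed set in section 3.4.1 ("Modified ITT (mITT) is composed of all ITT subjects who received at least one tablet of IP (placebo or acoziborole"), analysed as randomised), but section 5 assigns it no TEAE analysis.

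**The concern.** Having a PK sample is settled after dosing, and early death, early withdrawal or two missed samples can each prevent it. Membership of the primary safety population can then depend on something that harm itself might cause. Protocol 3.3 reports that 97.7% of related TEAEs in the pivotal study arose within 5 days of dosing, so most related events would fall before or around the first qualifying sample.

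A subject outside the set can still have recorded events. After withdrawal of consent the protocol stops data collection "with the exception of safety data, which should be collected if possible and in accordance with subject consent".

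At stake is less the overall TEAE rate than the uncommon event, which is what the 900 acoziborole subjects were chosen to reveal.

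**Working it through.** **1. The plan's own figures.** Inputs are 900 acoziborole and 300 placebo subjects (protocol 10.1.1). The chance of at least one event is 1 − (1 − p)^n. With n = 900:

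- p = 0.5%: 98.90% (stated 98%)
- p = 0.2%: 83.50% (stated 83.5%)
- p = 0.1%: 59.36% (stated 59.36%)

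The exact (Clopper-Pearson) 95% interval is 0.0028% to 0.617% for 1/900 and 0.069% to 0.971% for 3/900, in line with protocol Table 5. These figures assume that all 900 dosed subjects are counted.

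**2. Who is left out.** The protocol set is randomised and at least one tablet. The SAP set adds an available PK sample, and sampling is at Day 5 and Month 1 only (protocol 8.3.4). The difference is dosed subjects with neither sample. The SAP's additional run removes misallocated subjects from the same Safety Set, so it restores nobody.

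**3. One uncommon event.** Suppose the only acoziborole case in a Safety Set category is unsampled.

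- All dosed: 1/900 = 0.11%, exact 95% CI 0.003% to 0.62%
- SAP set: 0/899 = 0%, exact 95% CI 0% to 0.41%

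**4. Any TEAE.** If k unsampled acoziborole subjects all had an event (the worst case), the arm's rate falls by x/n − (x − k)/(n − k), with n = 900 and x = 900p. The documents give no TEAE rate, so p is assumed:

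| k | p = 2% | p = 20% | p = 50% |
|---|---|---|---|
| 1 | 0.11 points | 0.09 | 0.06 |
| 5 | 0.55 | 0.45 | 0.28 |
| 10 | 1.10 | 0.90 | 0.56 |

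For scale, the Newcombe/Wilson 95% CI for the excess rate at 450/900 against 150/300 is −6.50 to +6.50 points. At 449/899 it is −6.56 to +6.44.

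**5. Preferred-term thresholds (SAP 5.1).** For the excess-rate and NNT comparison (at least 1% in one group), 9/900 = 1.00% qualifies and 8/899 = 0.89% does not. The term then drops out only if placebo is also below 1%. For the CMH test (above 1%), one removal from the smallest qualifying count changes nothing: 10/900 = 1.11% becomes 9/899 = 1.001%.

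**6. Loss unrelated to events.** With 890 subjects instead of 900, detection of a 0.1% event is 1 − 0.999^890 = 58.95%, against 59.36%. Random loss is immaterial; only loss linked to the event matters.

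**The case against.** **The case for the SAP.** Once misallocation had been found, the treatment of an unsampled subject could not be verified, and a fallback to the randomised arm mixes two attribution rules. Few subjects can be affected. Entry requires agreement to at least 5 days in hospital, the end-of-hospitalisation visit may run to Day 8, Month 1 is a fallback, and the PK set asks only that a sample be available. A subject who falls ill early is more likely to be on the ward than gone. SAP 4.1 already promises a listing of excluded subjects with reasons. The listings of fatal, serious and grade 3 or higher TEAEs (SAP 5.1) and the SOC/PT tables (SAP 5.2.2) name no population, so the event may well be visible there. The table shells are attached separately and cannot be checked here.

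**What stands.** The small number and the planned disclosure stand, and they keep this a minor point. They do not remove it. Misallocation is a reason to assign treatment by PK, not to omit unsampled subjects with no all-dosed analysis alongside. A listing does not return an event to the excess rate, NNT, CMH or severity-category results.

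**Stronger readings that the documents do not support.**

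- A reader might infer that SAP 5.1 contradicts itself because its first-period denominator is subjects with at least one tablet. But 5.1 introduces the period breakdown as part of the analysis run on the Safety Set, and every member of that set took a tablet, so the two can be read as consistent.
- A reader might infer that the protocol 9.2 reason for not replacing lost subjects collapses. Loss there means missing the 4-month visit and being out of contact. Most such subjects would already have a Day 5 or Month 1 sample, so the reason fails only for those with neither.
- A reader might infer that the primary result is materially biased. Nothing in the documents shows that, and the any-TEAE figures above point the other way.

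**Conclusion.** The departure is clear from the text: the protocol's Safety Set is all dosed subjects, and the SAP's is dosed subjects with a PK sample. The SAP does not flag the change, and its text plans no TEAE analysis that brings the excluded subjects back.

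The importance is minor. The overall excess rate would shift by about 0.06 to 0.11 points per excluded acoziborole subject with an event, over assumed TEAE rates of 50% down to 2%. The residual risk is an uncommon serious or severe-and-related event in an unsampled subject, where a Safety Set rate of 1/900 would read 0/899. That example requires the only case to be the unsampled one.

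The verdict assumes the planned arm sizes. The number of dosed subjects without a sample is not given; that it is very small is inferred from hospitalisation and the Month 1 fallback.

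**What to change.** Either of two changes is enough.

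1. **Restore the protocol set.** Define the Safety Set as all randomised subjects who received at least one tablet. Assign actual treatment by PK where a result exists and otherwise by randomised arm, with a flag. Keep the PK-confirmed set as a sensitivity analysis.
2. **Keep the SAP set and add one run.** Repeat the primary TEAE table on the mITT set already defined in SAP 3.4.1.

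Under either, let the SAP 4.1 summary of analysis sets show the number of dosed subjects without a PK sample by randomised arm and reason.

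**Cost.** The work is a wording change, one flag and one extra run of the primary table. Under option 1, treatment received cannot be PK-verified for the few unsampled subjects, so some could be counted in the wrong arm. Under option 2, the misallocated subjects are also counted in their randomised arm, so that table should be read beside the PK-based one.
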